7.2 Definitions of Final Month and Final Visit

Final Month is defined as the last 28 days prior to and including the Reference Day, which is defined as the last visit date in the treatment period (last treatment visit date) or the last dose date if there is evaluable Alkaline Hematin (AH) data after the last treatment visit date and prior to or on the last dose date.

Final Visit is defined as the last non-missing assessment during the Treatment Period.

Post-Treatment Final Visit is defined as the last non-missing assessment during the Post-Treatment Follow-up Period.

7.3 Definition of Study Days (Days Relative to the First Dose of Study Drug) and Study End Days (Days Relative to the Last Dose of Study Drug)

For randomized subjects who received at least one dose of study drug, the study day is defined as the number of days since (positive values) or prior to (negative values) the first study drug dose. The day of the first study drug dose is defined as Study Day 1 while the last day prior to the first dose of study drug is defined as Study Day -1. There is no Study Day 0. Study end days are calculated based on the number of days relative to the last dose of study drug. The first day following the last dose of study drug is defined as Study End Day 1.

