5.4.1 Discontinuation of Individual Subjects

In the event that a subject withdraws or is prematurely discontinued from study drug treatment, the subject should complete the Treatment Period Premature Discontinuation Visit as soon as possible (preferably within 2 - 7 days of last dose of study drug, if possible) and undergo study procedures as outlined in Appendix C. Subjects who prematurely discontinue during the Treatment Period are expected to enter the 12-Month Post-Treatment Follow-Up Period.

In the event that a subject withdraws or is prematurely discontinued during the Post-Treatment Follow-Up period, the subject should complete the Post-Treatment Premature Discontinuation Visit as soon as possible and undergo study procedures as outlined in Appendix C. These procedures should not interfere with the initiation of any new treatments or therapeutic modalities the Investigator determines are necessary to treat the subject's condition. The reason(s) for the discontinuation from the study will be recorded in the eCRFs.

All used and unused study drug containers will be returned to the study site.

If a subject becomes pregnant during the Treatment or Post-Treatment Follow-Up Periods, no additional study procedures, except an ultrasound will be conducted. Refer to

Section 6.1.6 for instructions on reporting of a pregnancy to the Sponsor and the required follow-up on the subject/fetus and live births.

Subjects who prematurely discontinue from treatment and enter Post-Treatment Follow-Up and received study drug for < 3 months or the procedure was performed in the past two months are not required to undergo the following procedures during the Post-Treatment Period, unless requested by the AbbVie TA MD or based on clinical judgment:

Post-Treatment Period Month 3:

- TAU/TVU
- MRI

Post-Treatment Period Month 6:

- TAU/TVU
- DXA (unless the premature discontinuation was related to BMD decrease or the occurrence of a fracture)

If a subject is discontinued from the study with an ongoing adverse event or an unresolved laboratory result that is clinically significant (as determined by the Investigator), the Investigator will attempt to provide follow-up until a satisfactory clinical resolution of the laboratory result or adverse event is achieved.

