The Uterine Bleeding Questionnaire (UBQ) is to be completed by Site Staff at every scheduled monthly visit (or d. PCV) only if the subject did not return a sanitary product collection keg at the visit.

Once eligibility for entry into the extension study has been determined:

Subject Entering the Extension Study:

• Subject will return to the study site as soon as possible

- Subject will discontinue taking study drug from the pivotal study just prior to entering the extension study, i.e., subjects are to continue taking study drug until they have returned to the site for their roll-over visit
- Record transition of study subject into the extension study in IRT

Subject NOT Entering the Extension Study:

- Subject will discontinue taking study drug
- Subject will return to the study site as soon as possible
- Record transition of study subject into the Post-Treatment Follow-up Period in IRT
- The next scheduled visit will be the Month 1 Site Visit

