8.1.7 Efficacy

8.1.7.1 Primary Efficacy Variable

8.1.7.1.1 Primary Analysis

The primary analysis of the primary endpoint will be performed using the mITT analysis set.

The primary endpoint will be the percentage of subjects meeting a composite endpoint consisting of two bleeding assessments:

- Menstrual blood loss (MBL) volume < 80 mL during the Final Month (the last 28 days of treatment), and
- 50% or greater reduction in MBL volume from baseline to the Final Month (the last 28 days of treatment).

A subject who prematurely discontinues the study drug due to adverse events, "lack of efficacy," or "requires surgery or invasive intervention for treatment of uterine fibroids" will be considered as a non-responder regardless whether she meets the two aforementioned responder criteria or not.

Baseline MBL volume is described in Section 8.1.5. The Final Month is defined as the last 28 days of treatment prior to and including the last dose date.

The MBL volume used for the primary and sensitivity analyses is defined as the total combined volume of blood ascertained via the AH method from all used (validated and non-validated) sanitary products that a subject returns. In case a subject does not return any used sanitary products and indicates on the UBQ that she experienced bleeding during the Final Month, the MBL volume will be imputed per the procedure described in Section 8.1.7.1.2.

The primary endpoint will be analyzed using a logistic regression model including treatment as the main effect and baseline MBL volume as a covariate.

[figure not shown]

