7.4 Definition of Analysis Window

7.4.1 Treatment Period

Data obtained more than 3 days after the subject's last dose of study drug in Study M12-815 will be excluded for all assessments performed at periodic intervals (monthly, every 3 months, or every 6 months) in the Treatment Period with the following exceptions:

1. For BMD, TVU/TAU, MRI, and endometrial biopsy assessments, data obtained more than 28 days after the last dose of study drug in Study M12-815 will be excluded from summaries/analyses in the Treatment Period.
2. For Alkaline Hematin (AH) data, data obtained after the last dose of study drug in Study M12-815 will be excluded from the summaries/analyses in the Treatment Period.

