7.6.1.1 Observed MBL Volume Over a Window

If there were observed AH data between two study visits (Product Collection Visit or site visit with UBY completed), then the MBL volume on the days with observed AH data will be the observed AH data and the MBL volume for the rest of days between the two study visits will be imputed as 0 by AH data.

UBQ responses indicate if a subject has any bleeding or spotting since the last study visit (Product Collection Visit or site visit with UBQ completed). If observed evaluable AH data is available over a window, then the UBQ will not be used.

If the AH data is reported as "NVB" (no visible blood, discarded without assay), "NO BLEED" (no collection due to no bleeding as indicated by subject or clinical site on assay requisition form), or "TL BQL" (total below low limit of quantitation), the numeric value for the AH data will be imputed as 0. If the AH data is reported as other character value ("NULL," "IN ERROR," "NO DATA," and etc.), the corresponding numeric value for the AH data will be set as missing.

The observed MBL volume over a window (such as the Final Month, Month 1 [Study Days 2 – 28], Month 2 [Day 29 – Day 56], Month 3 [Day 57 – Day 84], Month 4 [Day 85 – Day 112], Month 5 [Day 113 – Day 140], and Month 6 [Study Days 141 – 168]) is defined as follows:

- If a subject has any evaluable AH data reported in the window, then the subject's MBL volume in this window will be the total combined observed AH data of validated and non-validated sanitary products over this window.
- If a subject is missing AH data or all AH data are unevaluable in the window and the UBQ is completed and indicates no bleeding or spotting, "Subject only had spotting that did not require the use of sanitary products" or "There was no visible blood on the sanitary products" and covers this window, then:

A value of 0 will be assigned to the MBL volume over this window.
- If a subject is missing AH data or all AH data are unevaluable in the window and the UBQ is completed with no bleeding or spotting or "Subject only had spotting that did not require the use of sanitary products" or "There was no visible blood on the sanitary products" indicated but UBQ does not cover the full window, then:

A value of 0 will be assigned to the MBL volume over this window if the days not covered by UBQ response as described above have AH imputed MBL volume (see first paragraph in Section 7.6.1.1) being 0 for those days.

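### For women who stop drug before their last treatment visit, SAP 7.2 runs the Final Month past the last dose while SAP 7.4.1 discards blood-loss data from those days, so responder status is overstated in a limited group

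*SAP*

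**What the plan says.** Protocol 8.1.7.1.1 ties the window to dosing: "The Final Month is defined as the last 28 days of treatment prior to and including the last dose date".

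SAP 7.2 ties it to a visit. The Final Month is the 28 days up to and including the "Reference Day, which is defined as the last visit date in the treatment period (last treatment visit date"). There is one exception: the Reference Day moves to the final dose when evaluable AH data exist later than that visit and no later than that dose. That exception covers a last dose after the last visit. Nothing covers a last dose before it.

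Three other rules interact with this one:

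- Protocol 5.4.1: a woman who stops drug early is to have a discontinuation visit, which the protocol places in the Treatment Period by name, "preferably within 2 - 7 days of last dose of study drug, if possible". No upper limit is set. Appendix C lists this visit as a column of the Treatment Period.
- SAP 7.4.1: for AH, "data obtained after the last dose of study drug in Study M12-815 will be excluded from the summaries/analyses in the Treatment Period". AH has no grace period; other periodic assessments have 3 or 28 days.
- SAP 7.6.1.1: if any AH data in the window are evaluable, the volume is their sum and the Uterine Bleeding Questionnaire (UBQ) is not used. When AH data were observed between two visits, "the MBL volume for the rest of days between the two study visits will be imputed as 0 by AH data". Nothing is rescaled for uncovered days.

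Under SAP 11.2.1, women whose primary reason for stopping is an adverse event, lack of efficacy, or surgery or invasive intervention for fibroids are non-responders whatever their volume.

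**The concern.** Take a woman whose discontinuation visit falls *k* days after her last dose. Her Final Month holds 28 − *k* on-drug days and *k* off-drug days. Bleeding on the off-drug days is discarded even if she returned the products. The *k* earliest on-drug days that the protocol would have counted are also lost. The shortened total is still judged against 80 mL and against half of a baseline built from whole menses.

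The SAP's own wording suggests this was not intended. SAP 11.2.1, the LOCF rule in 11.2.3.1 and the amenorrhea rule in 11.3.2.1 all speak of days of treatment, or on study drug, up to and including the Reference Day. SAP 11.2.2.1 also picks the imputation month from the Reference Day, so a late visit can select a month that lies largely after treatment.

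At stake are the primary endpoint and ranked endpoints 1 (change in MBL to the Final Month) and 2 (suppression of bleeding). The two ranked endpoints describe no non-responder rule. Sensitivity analysis 1 drops that rule and so is also more exposed. None of the five sensitivity analyses varies the Reference Day, so none would reveal the effect.

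**Working it through.** **Planned power, for scale.** Inputs from SAP 4.3: 100 placebo, 200 combination, 30% versus 60%; two-sided 0.05.
- Standard error under the null: √(0.5 × 0.5 × (1/100 + 1/200)) = 0.0612.
- Standard error under the alternative: √(0.3 × 0.7/100 + 0.6 × 0.4/200) = 0.0574.
- (0.30 − 1.96 × 0.0612)/0.0574 ≈ 3.13, so power is 99.9%. The stated figure of at least 90% holds.

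**Days lost.** On-drug days counted = 28 − *k*.
- *k* = 2: 26 days; 2/28 = 7.1% zero by rule.
- *k* = 7: 21 days; 7/28 = 25%.
- If bleeding were spread evenly, a true 28-day loss of up to 80 × 28/26 = 86 mL, or 80 × 28/21 = 107 mL, would pass the 80 mL limit.

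**A case.** Last dose Day 90, menses on Days 63–70 and again from Day 91, discontinuation visit Day 97. The protocol window is Days 63–90 and holds the whole menses. The SAP window is Days 70–97 and counts only Day 70.

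**How often half a menses or less is retained.** Assumed: 28-day cycle, random phase, 7-day menses with daily shares 10/25/25/15/10/8/7%. For each of the 28 phases, add the shares that fall on retained days. At *k* = 2 the only such phase puts days 2 and 3 of menses in the gap, leaving 100 − 25 − 25 = 50%. The last column adds the 80 mL limit for an assumed 250 mL menses, where the retained share must be below 80/250 = 32%.

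| Gap (days) | Phases with 50% or less | Of these, some AH data left | Some AH data left and below 32% |
|---|---|---|---|
| 2 | 1/28 = 3.6% | 1/28 = 3.6% | 0 |
| 3 | 3/28 = 10.7% | 3/28 = 10.7% | 0 |
| 4 | 4/28 = 14.3% | 4/28 = 14.3% | 2/28 = 7.1% |
| 7 | 7/28 = 25.0% | 6/28 = 21.4% | 4/28 = 14.3% |

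The third column is the mechanism at issue. With no AH data left, the value comes from the UBQ or multiple imputation.

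**Responder shift among affected women.** Illustrative simulation, all inputs assumed: 28-day cycle, 6-day bleed, lognormal volumes. From a 2-day to a 7-day gap:
- placebo-like group: 24% rises to 28% and 42%;
- active-like group: 61% rises to 64% and 72%.

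The simulation scores empty windows as 0 mL. At a 7-day gap, 2 of 28 phases are empty, so up to 2/28 × (1 − 0.24) = 5 of the 18 placebo-like points come from that shortcut.

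**Arm level.** Shift = share stopping early × share of those outside the three reasons × shift per affected group. The first two are assumed at 10–30% and 30–60%, the third at 3–20 points.
- Low: 0.10 × 0.30 × 3 = 0.09 points.
- High: 0.30 × 0.60 × 20 = 3.6 points.

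If all 3.6 points fell on placebo alone (33.6% versus 60%), the same power formula gives (0.264 − 1.96 × 0.0612)/0.0586 ≈ 2.46, or about 99.3%.

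**The case against.** The strongest reply concerns which visits count. The SAP does not define a visit in the treatment period. SAP 7.4.1 and 7.4.2 move most periodic assessments made more than 3 days after the last dose into follow-up. If visits follow the same rule, the gap is at most 3 days and the 4- and 7-day rows do not arise. Protocol 5.4.1 and Appendix C point the other way, but the SAP does not settle it. This stands as a limit on size; it does not remove the conflict at 2 or 3 days.

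The affected group is also narrow. The non-responder rule protects the primary endpoint for its three stopping reasons. Women still dosing at Month 6 take the morning dose before the visit (Protocol 5.5.1), so their gap is about zero. Women lost to follow-up have no discontinuation visit, and pregnant women have no further procedures except ultrasound. Protocol 8.1.6 lets the SAP set time windows, so departure from the protocol is not decisive alone; the clash within the SAP is.

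A reader might go further on three points, without support from the documents:

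- *Half of women with a 14-day gap are misclassified.* On the same profile 14 of 28 phases retain 50% or less, but 8 of those 14 leave no AH data and go to the UBQ or imputation. That leaves 6/28 = 21.4%.
- *Ending the window at the last dose removes all such error.* That holds only for exact 28-day cycles. Only cycles over 38 days are excluded. With 32- or 35-day cycles, a window ending on the last dose still holds 50% or less in 4/32 = 12.5% or 7/35 = 20% of phases.
- *Women delayed at rollover are equally affected.* Protocol 5.4.4 says of those not entering the extension "Subject will discontinue taking study drug"; they then return and are recorded as moving to follow-up. Nothing makes that return a Treatment Period visit.

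**Conclusion.** The conflict holds on a plain reading. Where the last dose precedes the last treatment visit and some evaluable on-drug AH data remain in the window, 7% (2 days) to 25% (7 days) of the Final Month is zero by rule. Blood loss is understated. A reader might infer that the primary endpoint is understated too, but it is a percentage of responders, so it is overstated in these women.

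Under the assumed cycle and profile, the share of phases affected is about 4%, 11%, 14% and 21% at 2, 3, 4 and 7 days, and lower once the 80 mL limit applies. Gaps beyond 3 days require the broader reading of a treatment visit. No dropout rate is given; under the assumed ranges the arm-level shift is about 0.1 to 3.6 points.

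It is also tempting to say that the bias works only against the drug, because it is larger in women who still menstruate. The shift per affected woman may well be larger on placebo, but the net effect also depends on how many women in each arm stop for other reasons, which is unknown. It can go either way. Power is not at risk under these ranges. This should be fixed, but it does not by itself put the primary conclusion in doubt.

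**What to change.** In SAP 7.2 keep the current rule and add one sentence: if the last dose date precedes the last treatment visit date, the Reference Day is the last dose date. This agrees with Protocol 8.1.7.1.1. Keep the existing clause for AH data after the last visit and on or before the last dose. Apply the same Reference Day to suppression, amenorrhea, control of bleeding, LOCF and the choice of imputation month. It would help to state whether the Premature Discontinuation Visit counts as a treatment visit.

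Two simpler rules are worse. Always using the last dose date adds days after the last visit that no returned products or UBQ cover. Always using the earlier of the two dates discards on-drug AH data that the SAP deliberately keeps.

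The cost is one sentence and a date derivation from dates already collected. A few more women may fall to multiple imputation. Error from cycles longer than 28 days remains, as it does under the protocol's own window.

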7.4 Definition of Analysis Window

7.4.1 Treatment Period

Data obtained more than 3 days after the subject's last dose of study drug in Study M12-815 will be excluded for all assessments performed at periodic intervals (monthly, every 3 months, or every 6 months) in the Treatment Period with the following exceptions:

1. For BMD, TVU/TAU, MRI, and endometrial biopsy assessments, data obtained more than 28 days after the last dose of study drug in Study M12-815 will be excluded from summaries/analyses in the Treatment Period.
2. For Alkaline Hematin (AH) data, data obtained after the last dose of study drug in Study M12-815 will be excluded from the summaries/analyses in the Treatment Period.

7.4.2 Post-Treatment Follow-Up Period

For subjects who are not rolled over into the Extension Study M12-816 and continue to the Post-Treatment Follow-up Period, summaries for the Post-Treatment Follow-up Period will include data obtained more than 3 days after the subject's last dose of study drug for all assessments performed at periodic intervals (monthly, every 3 months, or every 6 months), with the following exceptions:

1. For BMD, TVU/TAU, and MRI assessments, data obtained more than 28 days after the last dose of study drug will be included in the summaries during the Post-Treatment Follow-up Period.
2. For AH data, data obtained after the last dose of study drug in Study M12-815 will be included in the summaries during the Post-Treatment Follow-up Period.

7.4.3 Details Regarding Visit Windows

For analyses in the Treatment Period, time points and corresponding time windows are defined based on the time of exposure to study drug starting from Study Day 1.

The time windows described in this section will not be applied to bleeding assessments including AH data and Uterine Bleeding Questionnaire (UBQ). Rules described in Section 7.4.1 and Section 7.4.2 will be applied prior to defining time windows. Data considered as in the Treatment Period are not considered in the Post-Treatment Follow-up

Period as described in Section 7.4.1 and Section 7.4.2. Any data considered as Baseline (see Section 7.1) will not be included in any post-baseline windows.

Table 1 will be used for analyses of endpoints collected monthly in the Treatment Period and Post-Treatment Follow-up Period.

Table 1. Analysis Time Windows for Non-Bleeding Measurements Collected Monthly

Visit	Nominal Day (Study Day)	Time Window (Study Days)
Month 1	28	> 1 – ≤ 42
Month 2	56	> 42 – ≤ 70
Month 3	84	> 70 – ≤ 98
Month 4	112	> 98 – ≤ 126
Month 5	140	> 126 – ≤ 154
Month 6	168	> 154 – ≤ 196

	Nominal Day (Study End Day)	Time Window (Study End Days)
Post-Treatment Month 1	28	> 3 – ≤ 42
Post-Treatment Month 2	56	> 42 – ≤ 70
Post-Treatment Month 3	84	> 70 – ≤ 98
Post-Treatment Month 4	112	> 98 – ≤ 126
Post-Treatment Month 5	140	> 126 – ≤ 154
Post-Treatment Month 6	168	> 154 – ≤ 182
Post-Treatment Month 7	196	> 182 – ≤ 210
Post-Treatment Month 8	224	> 210 – ≤ 238
Post-Treatment Month 9	252	> 238 – ≤ 266
Post-Treatment Month 10	280	> 266 – ≤ 294
Post-Treatment Month 11	308	> 294 – ≤ 322
Post-Treatment Month 12	336	> 322 – ≤ 366

Table 2 will be used for analyses of endpoints collected every 3 months in the Treatment Period. If there is a scheduled Month 1 visit for the endpoint (e.g., PGIC-MB and

PGIC-NBUFS), the first subtable will be used. If there is no scheduled Month 1 visit for the endpoint (e.g., TAU/TVU, creatinine phosphokinase, urinalysis, apolipoprotein A and B, UFS-QoL), the second subtable will be used.

Table 2. Analysis Time Windows for Non-Bleeding Measurements Collected Every 3 Months in the Treatment Period

Visit	Nominal Day (Study Day)	Time Window (Study Days)
Month 1	28	> 1 – ≤ 56
Month 3	84	> 56 – ≤ 112
Month 6	168	> 112 – ≤ 196

Visit	Nominal Day (Study Day)	Time Window (Study Days)
Month 3	84	> 1 – ≤ 112
Month 6	168	> 112 – ≤ 196

Table 3 and Table 4 will be used for analyses of endpoints collected at Month 6 (biopsy, MRI, BMD) in the Treatment Period.

Table 3. Analysis Time Windows for Non-Bleeding Measurements Collected Every 6 Months in the Treatment Period (BMD)

Visit	Nominal Day (Study Day)	Time Window (Study Days)
Prior to Month 3		>1 – ≤ 84
Between Month 3 and Month 6	84	> 84 – ≤ 140
Month 6	168	> 140 – ≤ 196

Table 4. Analysis Time Windows for Non-Bleeding Measurements Collected Every 6 Months in the Treatment Period (MRI and Biopsy)

Visit	Nominal Day (Study Day)	Time Window (Study Days)
Prior to Month 6	70	> 1 – ≤ 140
Month 6	168	> 140 – ≤ 196

Table 5 will be used for analyses of endpoints collected at Post-Treatment Month 1, 3, 6, 9, and 12 (e.g., vital signs, clinical safety labs including chemistry, hematology, lipid panel and urinalysis, apolipoprotein A and B). Table 6 will be used for analysis of endpoints collected at Post-Treatment Month 3 and 6 (e.g., TAU/TVU). Table 7 will be used for analysis of endpoints collected at Post-Treatment Month 3 (e.g., MRI). Table 8 will be used for analysis of endpoints collected at Post-Treatment Month 6 and 12 (e.g., BMD).

Table 5. Analysis Time Windows for Non-Bleeding Measurements Collected at Post-Treatment Month 1, 3, 6, 9, 12

	Nominal Day (Study End Day)	Time Window (Study End Days)
Post-Treatment Month 1	28	> 3 – ≤ 42
Post-Treatment Month 3	84	> 42 – ≤ 126
Post-Treatment Month 6	168	> 126 – ≤ 210
Post-Treatment Month 9	252	> 210 – ≤ 294
Post-Treatment Month 12	336	> 294

Table 6. Analysis Time Windows for Non-Bleeding Measurements Collected at Post-Treatment Month 3 and 6

	Nominal Day (Study End Day)	Time Window (Study End Days)
Post-Treatment Month 3	84	> 28 – ≤ 126
Post-Treatment Month 6	168	> 126 – ≤ 210
Post-Treatment Months 7 – 12		> 210

Table 7. Analysis Time Windows for Non-Bleeding Measurements Collected at Post-Treatment Month 3

	Nominal Day (Study End Day)	Time Window (Study End Days)
Post-Treatment Month 3	84	> 28 – ≤ 126
Post-Treatment Months 4 – 12		> 126

Table 8. Analysis Time Windows for Non-Bleeding Measurements Collected at Post-Treatment Month 6 and 12

	Nominal Day (Study End Day)	Time Window (Study End Days)
Prior to Post-Treatment Month 6		> 28 – ≤ 140
Post-Treatment Month 6	168	> 140 – ≤ 196
Post-Treatment Months 7 – 11		> 196 – ≤ 308
Post-Treatment Month 12	336	> 308

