5.4.4 Delays in Rollover into the Extension Study

Subjects may be required to remain in the Treatment Period following the completion of the Month 6 visit if results to determine eligibility into the Extension Study are not available at the time of the Month 6 visit. Subjects will return to the study site at the same 28-day monthly visit intervals if eligibility for the extension study has not been determined before then. Subjects will continue to take study drug until eligibility has been established. These visits will be documented as and registered as Unscheduled Visits. Sites should register Unscheduled Visits in IRT in order to obtain additional kits of study drug. Procedures/assessments to be performed during the Unscheduled Visit while the subject is waiting for the determination of eligibility into the extension study, are indicated in the Table 6.

Table 6. Schedule of Assessments - Delays in Roll-Over into Extension Study

Schedule of Assessments – Delays in Roll-Over into Extension Study			
Procedure	Perform Monthly		
Symptom-directed Physical Examination	X		
Vital Signs	X		
Clinical/Safety Laboratory Tests: Hematology, Chemistry ^a	X		
Urine Pregnancy Test ^b	X		
Endocrine Panel: FSH, LH	X		
Pharmacodynamic Sample (PD): Serum Estradiol (E2) and Progesterone (P)	Х		
Contraception Counseling and Dispense Contraceptives as necessary	X		
Dispense Sanitary Products and Collection Kits (Keg, Collection Bags etc.)	Х		
Collect and Return Sanitary Products	Х		
Register Visits in IRT	Х		
Study Drug: Dispense (D) and Return (R) ^c	Х		
Study Drug Accountability	Х		
Study Drug Compliance	Х		
Adverse Event Monitoring	X		
Concomitant Medication Monitoring	Х		
Questionnaires UBQ ^d	Х		
C-SSRS – Since Last Visit	Х		
HCRU	Х		

a. Eight (8) hour minimum fast for Clinical Safety Laboratory Tests; Chemistry and Lipid Panels.

A positive urine pregnancy test result must be confirmed with a quantitative serum pregnancy test. For any subject b. who has a positive serum pregnancy test result, a TVU must be conducted as early as possible in the first trimester in order to assess the gestational age and estimated due date. The subject will be discontinued from the study at the point the pregnancy was confirmed.

[figure not shown]
Urine pregnancy test must be negative prior to providing subjects with their next monthly supply of study drug. c.

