10.0 Study Drug Exposure

Exposure to study drug will be summarized for the safety analysis set. The duration (days) of study drug treatment will be summarized with the mean, SD, median, minimum, and maximum for each treatment group and overall. The duration of treatment is defined as the difference between the dates of the first and last doses of the treatment plus 1 day. The duration (days) of study drug treatment will also be summarized by treatment group and overall with number and percentage for the following categories: 1 – 28 days, > 28 – 56 days, > 56 – 84 days, > 84 – 112 days, > 112 – 140 days, > 140 – 168 days, > 168 – 196 days, and > 196 days.

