12.6 Endometrial Biopsy

The number and percentage of subjects in each category of endometrial biopsy results will be summarized at Baseline, Between Month 3 and Month 6, and Month 6 for each treatment group.

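### A repeat or late biopsy or pelvic scan after Study Day 196 stays in the Treatment Period but has no row in the endometrial and ultrasound/MRI safety tables

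*SAP*

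**What the plan says.** SAP 7.4.3 sets the windows: "Table 3 and Table 4 will be used for analyses of endpoints collected at Month 6 (biopsy, MRI, BMD) in the Treatment Period". Table 3 covers BMD, Table 4 covers MRI and biopsy, and the second part of Table 2 covers ultrasound. In each of these, and in Table 1, the Month 6 row ends at Study Day 196 and no later Treatment Period row follows. Post-Treatment Tables 5 to 8, by contrast, all finish with an open-ended row.

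SAP 7.4.1 is applied before the windows and decides which period a result belongs to. For BMD, ultrasound, MRI and biopsy, "data obtained more than 28 days after the last dose of study drug in Study M12-815 will be excluded" from Treatment Period summaries, so anything up to that limit is kept. SAP 7.4.3 adds: "Data considered as in the Treatment Period are not considered in the Post-Treatment Follow-up" Period.

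Both documents provide for long exposure. Protocol 5.4.4 states: "Subjects may be required to remain in the Treatment Period following the completion of the Month 6 visit", and "Subjects will continue to take study drug until eligibility has been established". It sets no maximum. SAP 10.0 has the exposure bands "> 168 – 196 days, and > 196 days".

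For reporting, SAP 12.6 has biopsy results "summarized at Baseline, Between Month 3 and Month 6, and Month 6 for each treatment group". During treatment, SAP 12.7 and 12.7.2 report at Month 3 and Month 6, and 12.7.1 reports cysts at each relevant visit. When several results share a window, SAP 7.4.4 takes the worst for BMD, ultrasound and MRI (rule 2). For biopsy it takes the one nearest the nominal day (rule 1).

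**The concern.** The period rule and the window tables do not meet. One keeps a result in the Treatment Period and away from the Post-Treatment tables; the other gives it no row once Day 196 has passed. A Final Visit or any-time summary would catch such a result, but the biopsy and pelvic imaging sections have none.

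The women concerned can include some whose Month 6 endometrial result was unresolved. Protocol 5.3.1.1 requires a repeat when the Month 6 biopsy fails or is insufficient and the endometrium exceeds the stated thickness, and women may stay on drug meanwhile. Endometrial biopsy is a named safety variable (Protocol 5.3.5) in a trial of estrogen/progestin add-back. One abnormal repeat missing from the by-arm table would matter even if very few women are affected.

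**Working it through.** **Inputs.** Nominal Month 6 is Day 168 and the last Treatment Period window closes on Day 196 (SAP Tables 1 to 4). Biopsy, imaging and DXA are kept to last dose + 28 days (SAP 7.4.1). The Month 6 procedure window is −15/+4 days and the Month 6 visit window is −4/+6 days (Protocol Table 1). Monthly visits are scheduled from Day 1 (Protocol 5.1).

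**1. The plan's own limit.** 168 + 28 = 196, which matches the tables. The SAP does not say that the limit was derived this way.

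**2. Uncovered days.** For a last dose on Day L, data are kept to Day L + 28 and windows end at Day 196. The uncovered span is (L + 28) − 196 = L − 168 days.

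| Last dose (Day) | Kept to (Day) | Days without a row |
|---|---|---|
| 168 or earlier | 196 at most | none |
| 169 | 197 | 197 (1 day) |
| 174 | 202 | 197–202 (6 days) |
| 196 | 224 | 197–224 (28 days) |
| 224 | 252 | 197–252 (56 days) |

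Post-Treatment Tables 6 to 8 start after Study End Day 28, so they cannot take these results. No Post-Treatment table names biopsy.

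**3. On-schedule procedures.** 168 − 15 = 153 and 168 + 4 = 172. All fall inside the Month 6 windows, at least 196 − 172 = 24 days before they close.

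**4. Held-over visits.** Counted from Day 1, the first is nominally Day 168 + 28 = 196, on the boundary, and a second is Day 224. Protocol Table 6 lists no biopsy, ultrasound, MRI or DXA at these visits. The exposed data are therefore repeat or late procedures only.

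**5. Fallback outputs.**
- DXA: Final Visit, worst T- and Z-score at any time, and a listing of decreases of 8% or more (SAP 12.4.1). A late scan is lost only from the Month 6 row.
- Ovarian cysts: a listing of significant findings (12.7.1), but no row in the count by arm.
- Endometrial thickness and the other ultrasound/MRI values: by visit only (12.7, 12.7.2).
- Biopsy: by visit only (12.6).

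**6. Biopsy selection inside the window.** An on-schedule first sample lies at most 168 − 153 = 15 days from Day 168. A repeat on Day 184 or later is at least 184 − 168 = 16 days away, so rule 1 always prefers the first sample, even if it was insufficient. After Day 196 the repeat is at least 29 days away. This assumes that an insufficient sample counts as an assessment; the SAP does not say.

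**7. Labels.** SAP 12.6 uses a time point lying between Months 3 and 6. Table 4, which governs biopsy, has only a row for everything before Month 6 (Days 2 to 140) and a Month 6 row. The 12.6 label belongs to Table 3, which is for BMD.

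**The case against.** The strongest reply is that little data can fall in the gap. Hold-over is mainly a wait for results, and a result reported late keeps its in-window procedure date. That stands, and it limits the point to repeat or late procedures.

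It can also be said that a Month 6 window of Day 168 ± 28 is sensible, and that SAP 4.4 confines the end-of-treatment analysis to data from the 6-month treatment period. The bounded window is indeed defensible, especially for BMD, where rule 2 takes the worst scan and an open window would let longer-exposure scans replace Month 6 values. But no section excludes data after Day 196, 7.4.1 keeps them, and Protocol 5.4.4 counts the waiting time as Treatment Period. If exclusion is meant, the SAP should say so.

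Finally, abnormal findings reported as adverse events are tabulated to 30 days after the last dose (SAP 12.2), and Appendix Q includes endometrial biopsy results in surveillance. A reader might infer that late findings vanish altogether; these outputs show that they do not. They still do not put a late biopsy into the 12.6 table by arm.

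**Conclusion.** The gap holds in a limited form. Under the stated rules, a biopsy, ultrasound or MRI after Day 196 and within 28 days of the last dose is Treatment Period data with no row in 12.6, 12.7, 12.7.1 or 12.7.2. Rule 1 of 7.4.4 can also set aside a repeat biopsy inside the window. The primary endpoint is untouched.

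Three stronger readings are tempting, and the documents do not support them:
- **A sizeable number of women is affected.** No hold-over rate, repeat rate or count is given, and attending a held-over visit generates no biopsy or scan. Any figure would be a guess.
- **Women finishing normally lose data.** A last dose on Day 174 leaves six uncovered days, but no biopsy, imaging or DXA is scheduled in them.
- **The BMD conclusions are compromised.** Late DXA is missing only from the Month 6 row and remains in the other BMD summaries.

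The conclusion rests on applying 7.4.1 before the windows, as 7.4.3 directs, and on reading 7.4.4 literally. It is worth correcting because it concerns the by-arm display of endometrial safety and the remedy is cheap.

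**What to change.** 1. Leave the Month 6 windows bounded at Day 196. Opening them would not rescue a repeat biopsy, because rule 1 would still choose the sample nearer Day 168.
2. Add a worst-on-treatment row (or a Final Visit row) to SAP 12.6, 12.7.1 and 12.7.2, covering all data kept under 7.4.1.
3. Exempt biopsy from rule 1 of 7.4.4 so that the worst adequate sample is used. This needs a pre-specified ranking of the biopsy categories and a statement that an insufficient sample does not displace an adequate one.
4. Align the intermediate time point in 12.6 with the row in Table 4.

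The cost is SAP wording and one extra row per table. A few values in those rows will come from longer exposure than six months, which a footnote can state.
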